## ***21.7 Preventing and managing adverse events***

(1) Before treatment, all of the parents were advised by investigators of the potential risk of side effects and educated on relative evocative signs, which included but were not limited to weakness, unusual tiredness, losing consciousness, trouble awakening, difficulty feeding, respiratory difficulty, and severe diarrhea.

(2) To avoid the risk of hypoglycemia, we requested that  $\beta$ -blockers should be administered within 30 min after the patients were fed. The patients' parents were instructed to ensure that their children were free to eat as often they desired. If there were any possible hypoglycemia alteration, the parents were instructed to administer oral liquids containing sugar and seek medical support in the case of persistence of these signs.

(3) In patients in whom severe complication symptoms were observed, medical support from site investigators or pediatricians was sought immediately.

(4) In cases of mild hypoglycemia, bronchitis with dyspnea, bronchial hyperreactivity or mild to moderate bronchospasms, treatment was suggested to be temporarily discontinued based on the patients' symptoms.

(5) Mild CNS-related adverse effects (e.g., sleep disturbance and agitation) might have subsided without any interventions, or they often resolved when the treatment administration was altered (e.g., earlier evening dose or a decrease in daily dose). In patients associated with intolerable CNS-related adverse effects, discontinuation of  $\beta$ -blocker administration was recommended.

(6) Any dose reductions, interruptions, or cessations enacted at the discretion of the investigators were recorded.

## ***21.8 Termination of the study***

All participants were informed that they had the right to withdraw from the study at any time without prejudice to their medical care and that they were not obliged to state their reasons. Follow-up was considered complete when the participant completed all study procedures and assessments up to the 96-week visit. Termination of the study was mandatory in the following situations:

- Any grade  $\geq 4$  adverse event;
- Recurrent or persistent cases of hypoglycemia, bronchitis with dyspnea, bronchial hyperreactivity or bronchospasms.
- Persistent hypotension; or

---

-Persistent bradycardia.

### ***21.9 Outcome of the adverse event***

The outcome of an adverse event at the time of the last observation/assessment was classified as:

- (1) Recovered/resolved: All signs and/or symptoms of an adverse event disappeared without any sequelae at the time of the last observation/assessment.
- (2) Recovering/resolving: The intensity of signs and symptoms was diminishing and/or their clinical pattern was changing up to the time of the last observation/assessment in a way typical for its resolution.
- (3) Not recovered/not resolved: signs and symptoms of an adverse event had mostly unchanged or worsened at the time of the last observation/assessment.
- (4) Recovered/resolved with sequelae: actual signs and symptoms of an adverse event disappeared, but there were sequelae related to the adverse event at the time of the last observation/assessment.
- (5) Fatal: resulting in death. If there was more than one adverse event, only the adverse event leading to death was characterized as 'fatal'.

---

**22 Tapering and discontinuation of treatment**

Propranolol or atenolol were tapered and stopped at an appropriate time, which was primarily based on the response and lesion regression after treatment. In this trial, the treatment was tapered and discontinued on complete or nearly complete resolution of IH or if no further improvement of IH (for 12 weeks of observation) was observed after month 6. At the end of the treatment period, the drug dose was gradually reduced over 4 weeks and then cease. For more detail regarding the procedures for tapering and discontinuation of treatment, refer to the **Treatment** section.

## **23 Data management and quality assurance**

The site investigators were responsible for recording all study data in the patient report form. All of the clinical and laboratory data were entered in electronic format. The patient report form was completed as soon as possible after the clinical and laboratory data were collected, preferably on the day of the scheduled visit. Double data entry was performed, and the documents were compared. At the visit interval, the data entries were checked for completeness, and the documents were reviewed for errors. For more details regarding the procedures for digital photograph management and quality assurance, refer to the **Collection and Assessment of Series Digital Photographs** section. For more details regarding the procedures for adverse event collection, refer to the **Collection and Management of Adverse Event** section.

---

## 24 Missing data

If a patient dropped out of the study, the site investigators at the participant site attempted to ascertain the reason or reasons for the patient not continuing. If a patient missed one of the scheduled visits, the site investigators communicated with the parents or guardians to determine if the patient would come back for the next scheduled visit. As the trial progressed, missing data were monitored to ensure that there was not one data point that, for some reason, was routinely not being captured. If data were missing, the analyses were performed in several ways. The investigators first analyzed the data assumed to be missing completely at random. However, when the missingness depended on the outcome, the parameter estimation was most likely biased. The investigators would then assess the missing data mechanism according to the types of observed outcomes. When the missingness depended on the set of observed outcomes, a correctly specified covariance structure accommodated the situation. However, if the missingness was due to a primary outcome value that should have been obtained at week 24, the investigators performed a sensitivity analysis.

## 25 Statistical analyses

Statistical analyses were used to assess the recruitment, quality of data, and homogeneity of treatment groups and to evaluate the efficacy and safety of the treatments.

### 25.1 Descriptive methods

Continuous variables are described using the number of nonmissing values, mean (SD), mean (range), and median (interquartile range), as appropriate. For binary or categorical variables, absolute and relative frequencies (number and percentage) are provided. For comparisons between the groups, descriptive *P*-values are provided to show comparability of the groups in baseline characteristics and to provide a further descriptive measure.

### 25.2 Baseline characteristics

Both the propranolol and atenolol groups were characterized using descriptive methods based on the intention-to-treat principle. Table 1 gives an overview of what to describe at baseline in the intention-to-treat population.

### 25.3 Primary outcome analysis

Based on the intention-to-treat principle, the primary outcome analysis was performed in the intention-to-treat population. All patients treated with at least one dose of study medication (propranolol or atenolol) were included and analyzed in the group to which they were randomized.

Primary outcomes were analyzed by sensitivity analysis. Best-case (response) and worse-case (nonresponse) scenarios were evaluated based on the intention-to-treat principle (in the best-case scenario, missing data in the propranolol group were considered failures, and missing data in the atenolol group were considered successes). In addition, missing data in the propranolol group were considered successes, and missing data in the atenolol group were considered failures.

In addition, a per protocol analysis was performed. This means that only patients without major protocol violations are included. These patients fulfilled all inclusion and exclusion criteria and carried out all medical procedures/visits according to the protocol.

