## 12 Sample size determination

In this trial, propranolol was used as the control group to evaluate the efficacy and safety of the atenolol group (experimental group). The treatment response after 6 months of medication was used as the key therapeutic index. To calculate the sample size for this trial, we used the following assumptions:

- (1) A 2-sided 0.05 significance level;
- (2) Ratio of the propranolol group: atenolol group = 1:1;
- (3) A statistical power of 90%;
- (4) A 20% dropout rate due to ineligibility;
- (5) A follow-up of at least 96 weeks;
- (6) A 24-month recruitment period; and
- (7) In this trial, the atenolol group's evaluation variables were compared with the propranolol group's evaluation variables to test for noninferiority. The hypotheses are listed below:

-H0: Twenty-four weeks after therapy initiation, compared to the treatment response of propranolol therapy, that of atenolol was inferior; and

-H1: Twenty-four weeks after therapy initiation, compared to the treatment response of propranolol therapy, that of atenolol was non-inferior.

(8) Very limited data are available in the literature that can be used to set hypotheses for atenolol treatment. Existing case studies are mainly based on small single-center experiences. According to previous studies, propranolol's total treatment response is assumed to be 70-100%, and atenolol's total treatment response is assumed to be 70-100%. In addition, assuming that the atenolol on propranolol response rate does not fall by greater than 15%, the noninferiority margin was selected to be -15%.

(9) Assuming the ulceration rate in both groups to be 10%.

(10) A sample size of 180 patients was determined to be required for each group (a total of 360 patients).

[figure not shown]
[figure not shown]
---

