### 25.4 Secondary outcome analyses

Quantitative variables were compared with Student's unpaired t-test, paired t-test, Wilcoxon rank sum test (Mann-Whitney  $U$  test), or generalized linear mixed models (GLMM). GLMMs were employed to compare the difference between the two groups in HAS changes from baseline to 6 months. Categorical variables were analyzed with Fisher's exact test or a chi-square test, and 95% confidence intervals were calculated. Kaplan-Meier curves were used to visualize the time to treatment discontinuation.

All secondary outcomes were analyzed based on the intention-to-treat principle without imputation of missing values.

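### The noninferiority hypothesis and its -15% margin in Section 12 have no matching primary analysis, margin comparison or deciding result in Sections 24 and 25

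*Combined protocol and SAP*

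**What the plan says.** Section 12 frames the trial as a noninferiority comparison. Under its alternative hypothesis, at week 24, "compared to the treatment response of propranolol therapy, that of atenolol was non-inferior". It adds that "the noninferiority margin was selected to be -15" percent, and its design inputs include "A 2-sided 0.05 significance level", "A statistical power of 90" percent and 180 patients per group.

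Section 25.3 is the whole of the primary analysis section. It names the intention-to-treat population and then states: "Primary outcomes were analyzed by sensitivity analysis". Two scenarios follow. In the best case, missing outcomes count as failures on propranolol and successes on atenolol; the other scenario reverses this. A per-protocol analysis is added. The section gives no effect measure, test, interval, margin or success rule.

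Section 25.4, on secondary outcomes, has categorical variables analysed with Fisher's "exact test or a chi-square test, and 95% confidence intervals were calculated". It does not say what those intervals are for.

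Section 24 says that analyses with missing data are done in several ways, starting from missing completely at random, with a sensitivity analysis if missingness is due to the week-24 value itself. It does not make any of these primary.

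**The concern.** A noninferiority conclusion needs an estimated difference, a confidence limit and a stated comparison of that limit with the margin. The plan supplies the margin in Section 12 and none of the rest in Section 25.

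Two consequences follow. First, the only procedures that Section 25.3 describes for the primary outcome pull in opposite directions by construction, so the conclusion depends on which one is given weight. Second, an analyst looking for a named method would find only Fisher's exact and chi-square tests. These test equality. A nonsignificant result does not show noninferiority, and a significant one does not rule it out. The trial's main efficacy claim rests on a rule that the plan does not contain.

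**Working it through.** **Inputs.** From Section 12: margin -15 (taken here as absolute percentage points), two-sided 0.05, 90% power, "Ratio of the propranolol group: atenolol group = 1:1", 20% dropout, 180 per group. No single planning response rate is given in the readable text; it says that "propranolol's total treatment response is assumed to be 70-100%, and atenolol's total treatment response is assumed to be 70-100" percent. All response rates below are therefore illustrative.

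**Step 1: is the stated sample size compatible with the margin?** With equal true response p in both arms, n per arm = 2p(1-p)(1.960 + 1.282)² / 0.15².
- p = 80%: 0.32 × 10.51 / 0.0225 = 149.4, so 150; 150 × 1.2 = 180.
- p = 81%: 0.3078 × 10.51 / 0.0225 = 143.7, so 144; 144 / 0.8 = 180.

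So 180 per group fits a -15 point noninferiority design, but the rate actually used cannot be confirmed. With 20% lost, 144 per arm remain.

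**Step 2: what the two imputations do.** Take 180 per arm, 10% missing in each arm (half the planned dropout) and the same observed response r in both arms. In the worst case, atenolol = 0.9r and propranolol = 0.9r + 0.1, so the difference is -10 points. Lower limit = difference - 1.96 × √[(p₁(1-p₁) + p₂(1-p₂)) / 180].

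| Observed response | Proportions compared | 1.96 × SE (points) | Worst-case lower limit | Best-case lower limit |
|---|---|---|---|---|
| 80% | 72% v 82% | 8.6 | -18.6 | +1.4 |
| 90% | 81% v 91% | 7.1 | -17.1 | +2.9 |
| 95% | 85.5% v 95.5% | 6.0 | -16.0 | +4.0 |

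The worst case misses the margin in every row. The best case, a difference of +10 points, excludes zero in every row.

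**Step 3: what would happen if the Section 25.4 tests were carried over.** Exact enumeration over two independent binomials, with uncorrected chi-square and Wald limits. At a true 15-point deficit (propranolol v atenolol), the chance that chi-square is nonsignificant is:

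| True rates | 144 per arm | 180 per arm |
|---|---|---|
| 85% v 70% | 12.9% | 6.7% |
| 90% v 75% | 7.1% | 3.1% |
| 95% v 80% | 1.9% | 0.5% |

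In the same settings the margin rule (lower 95% limit above -15 points) passes about 2.5% to 3% of the time; at 95% v 80% the figures are 3.1% and 3.0%.

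The error also runs the other way. At a true 95% v 88%, atenolol is significantly worse by chi-square and yet within the margin in 26% of trials with 144 per arm and 45% with 180.

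**Step 4: single results with 180 per arm.**
- 144 v 130 responders (80.0% v 72.2%): difference -7.8 points, SE 4.48, lower limit -7.8 - 8.8 = -16.6; chi-square p = 0.084. Not significant, and not noninferior.
- 162 v 149 responders (90.0% v 82.8%): difference -7.2 points, SE 3.59, lower limit -7.2 - 7.0 = -14.3 (from unrounded values); chi-square p = 0.046. Significantly worse, and noninferior.

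**The case against.** The best defence is that Section 12 already implies the rule. It gives hypotheses, time point, significance level and margin, and most statisticians would read a 95% confidence interval compared with -15% into that. Section 25.4 also mentions 95% confidence intervals. This stands in part: the intended analysis can be guessed. But the guess leaves open the interval method, the governing population, how missing outcomes count and whether the margin is absolute. Section 12 speaks of atenolol's response rate not falling by more than 15% relative to propranolol, which could mean a ratio. At 80% on propranolol a relative 15% is 0.15 × 80 = 12 points, not 15. The intervals in Section 25.4 belong to secondary outcomes and are not tied to a response difference.

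A reader might infer that the plan prescribes an equality test for the primary outcome, so that a nonsignificant P value would stand in for noninferiority. The documents do not support this. Fisher's exact and chi-square tests are listed for secondary outcomes only, and Section 25.3 assigns no test at all. Step 3 is therefore conditional on a use that the plan never states.

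A reader might also infer that the margin is never used. It is set in Section 12, and the sample size is compatible with it; it is absent from the analysis sections. Two figures in Section 12 could not be read, and nothing is inferred from that.

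Finally, the false-noninferiority risk of an equality test depends on the response rate. At 95% v 80% chi-square is nonsignificant less often than the margin rule passes, so that harm disappears at high response rates.

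**Conclusion.** The gap is real and is one of omission: a confirmatory noninferiority hypothesis with no stated estimate, confidence limit, margin comparison or deciding analysis. It should be corrected, because the main efficacy claim depends on it.

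The firmest evidence of its size is the conflict between the two imputations that Section 25.3 does prescribe. At 10% missing per arm and equal observed response, they lead to failure of noninferiority and apparent superiority from the same data. That rests on 180 per arm, Wald limits, a margin in absolute points and observed response of 80% to 95%. The equality-test figures are secondary. They show what could go wrong if the tests in Section 25.4 were borrowed: 0.5% to 12.9% nonsignificant at a true 15-point deficit, and 26% to 45% significantly worse yet within the margin at 95% v 88%.

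**What to change.** Rewrite Section 25.3 to state:

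- The primary analysis is the difference in any-response proportion at week 24, atenolol minus propranolol, with a two-sided 95% confidence interval by a named method (for example Miettinen-Nurminen or Newcombe).
- It is done in one intention-to-treat set. Section 19 starts from all randomized patients and then excludes those never dosed or never evaluated; Section 25.3 includes anyone with at least one dose. A patient who was dosed but never evaluated is out under one and in under the other, so the two must be reconciled.
- One rule for missing week-24 outcomes is named as primary.
- Noninferiority is concluded only if the lower limit is above -15 percentage points. Section 12 should confirm that the margin is absolute.
- Fisher's exact and chi-square tests are not used to conclude noninferiority.
- The per-protocol analysis is reported as supportive, and the best and worst cases as sensitivity analyses.

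The cost is a few sentences of wording. No new data are needed, and the sample size does not change.

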## **9 Expected duration**

Research duration: 4 years.

Recruitment period: 2 years.

After enrolment, each study subject was followed up for 96 weeks following the start of study treatment.

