**16 Study visits**

Study visits were scheduled at enrolment; at 1, 4, 12, and 24 weeks after treatment; and then every 12 weeks until the end of the study or if there was any specific need after enrolment. Body weight, height, heart rate, blood pressure, blood glucose, full blood count, liver function tests, renal function and ECG were obtained during protocol visits and in-between periods if needed. All adverse events, which were identified by the investigators as at least possibly treatment-related during the 24-week treatment phase, were collected by the investigator. At each visit, the drug will be handed over to the parent/guardian in an amount sufficient to last the interim duration.

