## 19 Primary outcome measures

The primary outcome measure was the clinical response at 6 months in the intention-to-treat population. The intention-to-treat population was defined as all patients who had undergone randomization. If after assignment, a patient did not receive a drug administration or if an evaluation was never made after drug administration, the patient was excluded from the intention-to-treat population.

Digital photographs of IHs were independently obtained by three investigators who were unknown to the study group assignment. In the case of multiple IHs, only the most clinically important IH (typically the largest or most ulcerated IH) was documented.

Changes in IH size and color were classified as a complete response, nearly complete response, partial response or no response. The primary outcome measure was any response or nonresponse at 6 months in the intention-to-treat population of all patients who underwent randomization. The any response included compete, nearly complete and good responses; the nonresponse included stable or deteriorated:

-A complete response was defined as no redundant tissue or telangiectasia was identified.

-A nearly complete response was defined as a minimal degree of telangiectasis, erythema and skin thickening.

-A partial response was defined as a size reduction or change in color that did not meet the nearly complete resolution criteria.

-Stable was defined as no changes in size or color between baseline and month 6.

-Deterioration was defined as further growth of the target hemangioma.

Treatment failure was defined as patients withdrawing from trial treatment due to nonresponse and/or severe adverse events.

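### The per-protocol set is defined in two ways that differ, with no week-24 limit; read literally, missing any of six later visits excludes an infant with a valid primary outcome.

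*Combined protocol and SAP*

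**What the plan says.** Section 19 sets the endpoint and its population: "The primary outcome measure was the clinical response at 6 months in the intention-to-treat population". Section 25.3 makes the intention-to-treat analysis primary and adds best-case and worst-case handling of missing outcomes. It then continues: "In addition, a per protocol analysis was performed".

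Two statements define the per-protocol set. The first is that "only patients without major protocol violations are included". The second says that these patients met all eligibility criteria and "carried out all medical procedures/visits according to the protocol". Neither statement has a time limit. The plan contains no list of major violations, no visit window and no tolerance for a missed visit.

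Section 16 schedules visits "at 1, 4, 12, and 24 weeks after treatment; and then every 12 weeks until the end of the study". Section 9 says that "each study subject was followed up for 96 weeks following the start of study treatment", and Section 21.8 treats follow-up as complete once the participant has "completed all study procedures and assessments up to the 96-week visit". Under Section 18, photographs are taken at baseline and at weeks 1, 4, 12, 24 and 96, so none is scheduled from week 36 to week 84.

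**The concern.** The two statements select different infants unless every missed visit is a major violation, and the plan does not say that it is. Apart from eligibility, the all-visits clause is the only operational criterion given, so an analyst who follows the text would have to apply it or devise another rule. If that choice is made after the data are seen, the analysis loses much of its value as a check.

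The literal rule also selects on events after the outcome. A missed week-60 visit cannot change the week-24 response, yet it would remove the infant. The protocol itself gives reasons why late attendance may depend on response. Under Section 22, drug is tapered after month 6 when the lesion has resolved or nearly so, or has stopped improving. Under Section 16, drug is handed over at visits, so a family whose infant is off treatment has less reason to come. Under Sections 17.2 and 20.5, rebound leads to renewed treatment and so to more contact. Mandatory termination for adverse events under Section 21.8, if it occurs after week 24, could also leave later visits undone. If these processes differ between arms, the week-24 comparison in the per-protocol set is biased, and the direction cannot be predicted.

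This matters because Section 12 frames the hypothesis as noninferiority, and this is the only primary-outcome analysis restricted to compliant infants.

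**Working it through.** **Visit count.** From Sections 16, 9 and 21.8, the post-baseline visits are weeks 1, 4, 12, 24, 36, 48, 60, 72, 84 and 96, which is ten. Four run through week 24, and six come after it.

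**The plan's own figure.** Section 12 gives 180 per group from a 15-point margin, two-sided 0.05 (one-sided 0.025), 90% power, 1:1 allocation and 20% dropout. It states response only as a range of 70–100%, so 180 has no unique derivation. With n = (1.960 + 1.282)² × 2p(1−p) / 0.15²:

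- p = 0.80 gives 150, and 150 × 1.2 = 180.
- p = 0.81 gives 144, and 144 / 0.8 = 180.

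The figure of 180 therefore lies within what the inputs allow. It is used below only as the starting number per arm.

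**Assumption.** The documents give no missed-visit rate. Let m be the probability of missing any one visit, with misses independent.

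- Retained if four visits are required: (1−m)⁴
- Retained if all ten are required: (1−m)¹⁰
- Share of infants compliant to week 24 who are lost through the six late visits alone: 1 − (1−m)⁶
- Power = Φ(0.15 / √(2p(1−p)/n) − 1.960), with n = 180 × retention and equal response p in both arms

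**Results at p = 0.80:**

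| m | Retained to week 24 (per arm) | Retained to week 96 (per arm) | Lost through late visits alone | Power, four visits → ten visits |
|---|---|---|---|---|
| 1% | 96.1% (173) | 90.4% (163) | 5.9% | 0.937 → 0.923 |
| 2% | 92.2% (166) | 81.7% (147) | 11.4% | 0.927 → 0.895 |
| 5% | 81.5% (147) | 59.9% (108) | 26.5% | 0.894 → 0.786 |
| 10% | 65.6% (118) | 34.9% (63) | 46.9% | 0.822 → 0.556 |

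Worked line for m = 5%: 0.95⁴ = 0.815, 0.95¹⁰ = 0.599 and 1 − 0.95⁶ = 0.265. With ten visits, n = 107.8, the standard error is √(0.32/107.8) = 0.0545, and 0.15/0.0545 − 1.960 = 0.79, so Φ = 0.786.

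**Sensitivity at m = 5%:**

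- 70% response: 0.800 → 0.671.
- 90% response: 0.990 → 0.956.
- 80% response, starting from 144 per arm (180 × 0.8): 0.819 → 0.692.

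**The case against.** The strongest reply is that exclusion after one missed late visit is not the only reading. The sentence on major violations can be taken as the governing rule, with the next sentence loosely describing the resulting patients. The paragraph sits in a section about a week-24 outcome, so its visits may be meant as those bearing on that outcome. Section 24 deals with a missed visit by contacting the family about the next one and does not call it a violation. This stands. The documents establish an ambiguous rule with no time limit, not a settled exclusion rule.

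A reader might also infer that the per-protocol result is a key or co-primary test. The documents do not say so. It is an additional analysis, no decision rule depends on it, and no power is promised for it, so falling below 90% in this set breaches nothing in the plan.

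A reader might further infer that a sharp loss of power is established. It is not. At 1% missed the loss is small, and at 90% response it is small even at 5% missed. If misses cluster in the same families at the same per-visit rate, fewer infants are lost. The 20% dropout in Section 12 is attributed to ineligibility and cannot stand in for a missed-visit rate.

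What survives is the conflict between the two statements and the missing week-24 limit. The literal rule's selection on attendance after the outcome does not depend on any particular power figure.

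**Conclusion.** The point holds as an ambiguity with a real consequence. The per-protocol set has two definitions that do not agree, one rests on an undefined term, and neither stops at week 24. Under the literal reading, six of ten post-baseline visits can exclude an infant after the primary outcome has been observed, and the reasons for missing them may be related to response or adverse events.

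The count of six follows directly from the documents. The percentages and power figures do not: they rest on assumed independent miss rates of 1% to 10%, equal response in both arms and a start of 180 per arm. They show a loss ranging from minor to serious, and the documents cannot say where in that range the trial would fall. The direction of any bias is likewise unknown. The primary intention-to-treat analysis is not affected.

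**What to change.** In Section 25.3, delete the clause on all procedures and visits. Replace it with a closed list of major violations limited to baseline through week 24, for example eligibility breach, wrong drug received, or no week-24 photograph. Fix the list, and each infant's classification under it, blind to outcome.

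Add a carve-out. Section 17.3 counts the need for additional hemangioma-specific intervention as treatment failure, and Section 19 does the same for withdrawal from trial treatment because of nonresponse or severe adverse events. Infants who meet either definition by week 24 should stay in the per-protocol set as nonresponders, even without a week-24 photograph. Without this, a list that excluded infants for additional therapy, short exposure or a missing photograph could remove the protocol's own failures and so select directly on outcome.

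If the set has already been built, state which rule was used and report its size and result under both.

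The cost is a change of wording, with no new data, visits or patients. The downside is a slightly less strict set, because infants with incomplete attendance after week 24 remain in it.
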